The need to understand the impact of smoked THC and CBD in clinical populations is supported by 3 prior studies by Valerie Curran’s group at University College London. In a 2008 study, hair samples collected from a population of 140 users of a variety of illicit substances were screened for THC and CBD. Subjects who screened positive for THC alone showed higher levels of positive schizophrenia-like symptoms compared to both those who screened negative for cannabinoids and those who screened positive for THC and CBD, suggesting that smoked CBD may have antipsychotic properties. A second study in 2010 in which subjects were assessed after using their chosen strain of cannabis indicated that smokers of high CBD:THC strains showed a decreased attentional bias towards drug and food stimuli and less self-reported liking of cannabis stimuli. These data suggest that CBD may mitigate the effects of THC and may have utility as a treatment for cannabis dependence. Finally, in a 2014 study of 48 cannabis-using subjects who received inhaled THC, CBD, THC+CBD, and placebo, subjects showed improved recognition of facial affect without any effect on feelings of being “stoned” after receiving CBD alone. In contrast, THC produced a reduction in facial affect recognition, while THC+CBD and placebo showed no effect. Both THC alone and THC+CBD in combination increased feelings of being “stoned” relative to placebo. The results of this laboratory study provide early evidence that agents that target the endocannabinoid system may produce contrasting neurocognitive effects. In total, the findings from these studies suggest that further study of the impact of THC and CBD in psychiatrically ill populations (including OCD) is warranted.

Specific Aims and Hypotheses

Specific Aims and Hypotheses

Specific Aims:

To compare the effects of High THC (5-10%)/Low CBD (<1%) marijuana, Low THC (<1%)/High CBD (>10%) marijuana, and placebo (0% THC and CBD) marijuana in adults with primary OCD who also occasionally smoke marijuana.

Specific Hypothesis:

In the acute setting, smoked marijuana in both high THC/low CBD and low THC/high CBD concentrations will lead to a reduction in symptoms in adults with primary OCD who are also occasional marijuana smokers as compared to placebo.

Description of Subject Population

Sample #1

Specify subject population

Adults who meet DSM 5 criteria for OCD who are also occasional marijuana smokers

Number of completers required to accomplish study aims

15

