Subjects may be receiving either psychotherapy or medication management in the community while they participate in this study; however, they will not be eligible for participation in this study if they a) are taking a selective SRI or clomipramine and have altered their dose in the 6 weeks prior to study enrollment or are planning to make changes to their medications during the period of the study (approximately 3 weeks), b) are taking psychotropic medications other than selective SRIs or clomipramine, or c) have begun cognitive-behavioral therapy within 8 weeks prior to enrollment or plan to commence cognitive-behavioral therapy during the period of the study (approximately 3 weeks). For subjects who are not currently receiving any treatment for OCD and are interested, referrals for external treatment providers will be given.”

Eligible subjects who have finished other studies in the Anxiety Disorders Clinic will be offered participation if they are eligible. These protocols will include:

IRB#6628 Attaining and maintaining wellness in OCD

IRB#7000 Control and Reward Circuits in OCD

IRB#7127 Toward Precision Medicine for OCD

IRB#7059 Pilot study of personalized-computerized inhibitory control training for OCD

IRB#6837 Internet Based Treatment for OCD (iCBT)

IRB#7239 Cannabinoid Medication for Adults with OCD

IRB#7572 Feasibility, Acceptability and Preliminary Efficacy of a Mobile App (nOCD) for OCD

Inclusion/Exclusion Criteria

Name the subject group/sub sample

Adults with OCD

Create or insert table to describe the inclusion criteria and methods to ascertain them

- 1. Patient must be 21-55 years of age at the time of consent
Clinical interview
- 2. Patient must be physically healthy male or non-pregnant female. Females of childbearing potential must comply with contraceptive restrictions noted in the protocol.
Clinical interview by trained M.D. or Ph.D., physical examination by M.D., ECG, and blood tests
- 3. Patients must fulfill DSM 5 criteria for OCD, OCD being the principal disorder (i.e., currently the most severe and needing of treatment), and have had OCD for at least one year with near-constant symptoms.
Clinical Interview by trained M.D. or Ph.D. and results of SCID
- 4. Patients with a Y-BOCS score of greater than or equal to 16 prior to entering trial.
Clinical interview and assessment by trained rater
- 5. Patient has smoked marijuana at least once in the past and did not experience intolerable side effects.
Clinical Interview

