- 6. Patient has not smoked marijuana more than once per day over the preceding 8 weeks.
Clinical Interview and urine toxicology
- 8. Each patient must have a level of understanding sufficient to provide written informed consent to all required study tests and procedures.
Clinical interview
- 9. Women who are practicing an effective form of birth control (e.g. hormonal contraception or barrier methods).
Clinical interview

Create or insert table to describe the exclusion criteria and methods to ascertain them

- 1. First degree relative with schizophrenia
Psychiatric evaluation
- 2. Presence of psychotic symptoms or lifetime history of schizophrenia, bipolar disorder, substance-induced psychotic disorder, or psychosis due to a general medical condition.
Psychiatric evaluation/SCID
- 3. Current, eating disorder
Psychiatric

| | |
|---|--|
| | evaluation |
| 4. Major Depressive Disorder or other current psychopathology requiring medical intervention | Psychiatric evaluation |
| 5. Severely depressed patients with HDRS (Hamilton Depression Rating Scale) score greater than 25 or judged clinically to be at risk of suicide | Psychiatric evaluation/SCID and HDRS |
| 6. Female patients who are either pregnant or nursing | Clinical interview, medical examination, and blood pregnancy test |
| 7. Patients planning to commence cognitive-behavioral therapy during the period of the study or those who have begun cognitive-behavioral therapy within 8 weeks prior to enrollment | Clinical interview |
| 8. Patients receiving psychotropic medication other than clomipramine or selective SRIs. Patients taking clomipramine or a selective SRI must be on a stable dose for 6 weeks prior to study entry and must not plan to alter their regimen during the period of the study. | Clinical interview |
| 9. Patients who report using any illicit substances other than marijuana within 3 months prior to study entry or who have a urine toxicology screen positive for any substance other than marijuana. | Clinical interview |
| 10. Presence of significant medical illness (e.g. diabetes, cardiovascular disease, hypertension, clinically significant laboratory abnormalities, LFTs>1.5x upper limit of normal), resting blood pressure >140/90 | Medical history, physical examination, laboratory tests, 12-lead ECG, Mantoux test |
| 11. History of heart disease | Clinical interview, abnormal ECG |
| 12. Current parole or probation | Self-report during interview |

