- In the Investigator's opinion, are experiencing a clinically significant deterioration in OCD (i.e., 4-5 point change on the visual analogue scale for obsessions or compulsions and YBOCS score 10 points greater than their baseline at any time point).
- Commit a protocol violation, including lack of compliance.
- Are "lost to follow-up".
- Encounter other conditions (such as administrative issues or pregnancy).

If a patient discontinues from the study at any time at their own request or at the study doctor's discretion, the reason(s) for discontinuation are to be recorded by the study.

Blood and other Biological Samples

Please create or insert a table describing the proposed collection of blood or other biological specimens. We will perform urine pregnancy tests and urine drug screens prior to each laboratory session.

Assessment Instruments

Create a table or give a brief description of the instruments that will be used for assessment

1. Telephone Interview (10 minutes)
2. General Health Questionnaire (5 minutes)
3. Drug History Interview (30 minutes)
4. Drug History Questionnaire (10 minutes)
5. Medical History Questionnaire (10 minutes)
6. Psychiatric and Physical Examination (60 minutes)
7. Yale-Brown Obsessive Compulsive Scale (Y-BOCS, 15 minutes)
8. Structured Clinical Interview for DSM 5 (SCID, 1-2 hours)
9. 17 Item Hamilton Depression Rating Scale (HDRS-17, 5 minutes)
10. 14 Item Hamilton Anxiety Rating Scale (HARS-14, 5 minutes)
11. Marijuana Timeline Followback (TLFB, 3 minutes)
12. Yale-Brown Obsessive Compulsive Challenge Scale (YBOCCS, 1-2 minutes)
13. State Anxiety Questionnaire (STAI, 3 minutes)
14. Visual Analog Scale (VAS) (2 minutes): Modified from the OCD visual analog scale (Rodriguez et al. 2013) and Mood scale (Bedi et al. 2013) used in previous studies, this is a visual analog scale used to assess both subjective drug effects (physical symptoms, mood, anxiety) and OCD symptoms

15. Marijuana (Cannabis) Rating Form (MRF, 2 minutes): participants rate the strength, liking, desire to take again, good drug effect and bad drug effect of smoked marijuana

16. Qualitative Urinalysis (2 minutes)

17. Heart Rate and Blood Pressure (1 minute)

Please attach copies, unless standard instruments are used

Off label and investigational use of drugs/devices

Choose from the following that will be applicable to your study

✓ Drug

Select the number of drugs used in this study

1

Drug #1

Name of the drug

Marijuana

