Cannabis Effects: We will use a random-effects linear mixed model to evaluate changes in each continuous outcome (YBOCCS, OCD-VAS, STAI-S MRF, cardiovascular measures) as a function of condition (THC, CBD, placebo), time point, and their interaction. Mixed-effects modeling accounts for clustering of repeated measures within subjects, allows time to be modeled as a continuous rather than categorically, and has been used in similar acute pharmacological challenge studies (Rodriguez et al. 2013). The model will include participants as a random effect, condition and time as fixed within-subjects factors, the interaction between condition and time, and a random intercept. Given that the interval between sessions increases over the course of each session, we will model time as a continuous variable. We will use contrasts within each mixed-effects linear regression model to estimate differences in outcomes between both active cannabis varieties and placebo at different time points. All statistical tests will be conducted using an alpha level of 0.05, two-tailed.

Other Effects: Though we have no a priori hypotheses about the effects of age, gender, comorbid diagnoses (e.g. MDD), or other factors that might influence our participants' response to cannabis, we will nonetheless explore the possibility of such effects by including these factors as covariates in separate analyses.

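### Each active-placebo contrast is tested against an error term that ignores session-to-session variation and mixes in the third condition

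*Combined protocol and SAP*

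**What the plan says.** The Data Analytic Plan, under Cannabis Effects, fits one mixed model per outcome, with "participants as a random effect, condition and time as fixed within-subjects factors, the interaction between condition and time, and a random intercept". Both comparisons come from that fit, through "contrasts within each mixed-effects linear regression model to estimate differences in outcomes between both active cannabis varieties and placebo", at several time points. On time coding the plan says "we will model time as a continuous variable", and on error rates "All statistical tests will be conducted using an alpha level of 0.05, two-tailed".

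The plan does not mention a participant-by-condition (session) effect, a residual covariance, variances by condition, robust standard errors or a small-sample df method. A single residual variance is therefore the ordinary reading of the text, not a stated choice.

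The Data Analysis paragraph under Study Procedures describes a different method, a repeated-measures ANOVA with planned comparisons, and does not state the error term either.

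Each participant has one session per condition. Table 1 schedules one pre-dose rating and six post-dose ratings (20, 40, 60, 90, 120 and 180 minutes). Against "Number of completers required to accomplish study aims" the form gives 15, with 20 to be enrolled.

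**The concern.** The hypothesis has two halves: each active variety reduces OCD symptoms compared with placebo. Each half depends on its own standard error, and the stated model can get both wrong in two ways.

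- **Session clustering.** The six post-dose ratings of one session share whatever was particular to that participant on that day under that condition. A participant intercept does not absorb this. The model then treats the six ratings as independent information about the condition difference, and the standard error is too small.
- **Pooling over conditions.** One residual variance averages over all three conditions. If THC sessions are the most variable, the average is too small for THC-placebo and too large for CBD-placebo.

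The design makes unequal spread plausible without establishing it. Prior exposure may be slight ("Patient has smoked marijuana at least once in the past and did not experience intolerable side effects") or close to daily ("Patient has not smoked marijuana more than once per day over the preceding 8 weeks"). The same model is applied to a form on which "participants rate the strength, liking, desire to take again, good drug effect and bad drug effect of smoked marijuana", and ratings after 0% marijuana may sit near the floor. At stake is whether the two halves of the hypothesis are really tested at the stated 5%, and whether CBD-placebo loses power to noise from the THC sessions.

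**Working it through.** **Inputs from the documents.** n = 15 completers, m = 6 post-dose ratings per session, three conditions, two-sided 0.05. The documents give no SD, effect size or power, so the figure of 15 cannot be reproduced.

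**Assumptions.** SDs for THC:CBD:placebo are k:1:1. Session variance is q times the residual variance in every condition. There is no true effect. The contrast is averaged over the six post-dose ratings.

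**Step 1: pooling alone (q = 0).** The pooled variance is (k² + 2)/3. Model SE divided by true SE is
- THC-placebo: √[2(k² + 2) / (3(k² + 1))]
- CBD-placebo: √[(k² + 2)/3]

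The actual error rate is 2[1 − Φ(1.96 × ratio)].

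| k | THC-placebo ratio (rate) | CBD-placebo ratio (rate) |
|---|---|---|
| 1 | 1.000 (5.0%) | 1.000 (5.0%) |
| 1.5 | 0.934 (6.7%) | 1.190 (2.0%) |
| 2 | 0.894 (8.0%) | 1.414 (0.6%) |

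At k = 1 the nominal 5% is recovered. However large k is, the THC ratio cannot fall below √(2/3) = 0.816, a rate of 11.0%.

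**Step 2: add session variance and leave it unmodelled.** The residual df are 15 × 18 − 15 − 5 = 250, of which 28 lie between sessions. The expected residual mean square grows by the factor 1 + (28 × 6/250)q = 1 + 0.672q. The true variance of the contrast grows by 1 + 6q. Both ratios in step 1 are therefore multiplied by √[(1 + 0.672q)/(1 + 6q)].

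- k = 2, q = 0.25 (session SDs 1:0.5:0.5, residual SDs 2:1:1). The factor is √(1.168/2.5) = 0.684. THC: 0.894 × 0.684 = 0.611, about 23%. CBD: 1.414 × 0.684 = 0.967, about 6%.
- k = 1.5, q = 0.5 (session SDs 1.06:0.71:0.71, residual SDs 1.5:1:1). The factor is √(1.336/4) = 0.578. THC: 0.934 × 0.578 = 0.540, about 29%. CBD: 1.190 × 0.578 = 0.688, about 18%.
- k = 1, q = 0.5 (no inequality at all). Both ratios are 0.578, about 26%.

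Simulation with n = 15 agrees: 23-24% and 6% for the first case, 29% and 18% for the second.

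**Step 3: dependence on the time point.** The plan takes contrasts at different times. At 60 minutes with k = 1.5 and q = 0.5, the ratios are 0.58 and 0.74 (simulated rates 25% and 14%). At 60 minutes the CBD-placebo interval turns from too wide to too narrow once q exceeds about 0.11 (k = 1.5) or 0.28 (k = 2). For k = 1.5 the turn comes later at 20 minutes (0.28) and at 180 minutes (0.85).

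**Step 4: add a session term with one common variance.** Clustering is repaired and pooling is not. The contrasts now rest on a pooled error with 28 df. At SDs of 2:1:1 the simulated rates are 8.0% (THC) and 0.8% (CBD); at 1.5:1:1 they are 6.7% and 2.2%. For an effect that paired differences would detect with 80% power, the pooled analysis of CBD-placebo has 71% at 1.5:1:1 and 56% at 2:1:1.

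**Step 5: paired differences.** Each participant's active-minus-placebo difference, tested on 14 df, contains the session variance and excludes the third condition. Simulated error rates stayed within 4.5-5.4% in every scenario. With equal variances, power is 80% against 83% for the pooled test. The interval multiplier rises from 2.048 (28 df) to 2.145 (14 df), a ratio of 1.047.

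**The case against.** The strongest reply is that nothing in the documents shows THC sessions to be more variable. The 5-10% THC range is a product specification, and nothing says that potency varies between participants. Use history could alter the response to CBD or placebo as well. The drug-effect form is not an OCD symptom measure, and a floor after placebo would make placebo alone the low-variance condition, which is not 2:1:1. All of this stands, so the ratios above are illustrations.

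A second reply is that the common residual variance is inferred from silence, and that planned comparisons in an ANOVA can use a separate error for each contrast. This also stands, and is a reason to state the error term.

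A reader might infer that CBD-placebo error bars are simply too wide, with a false-positive rate below 1% whether or not a session term is fitted. The documents do not support this. For the model as written it holds at SDs of 2:1:1 only if session variance is zero, and modest session variance reverses it. It would also be falsely reassuring about a contrast that may reject too often. Differences in exposure history or sensitivity would moreover appear mainly as participant-by-condition variation, which the stated model omits.

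The objection does not remove the core. The session omission does damage even with equal SDs, and repairing it with a common variance leaves the pooling error in place.

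**Conclusion.** The concern holds in this form: as specified, each contrast's error term neither reflects session-to-session variation within a participant nor excludes the third condition. If THC sessions are the more variable, THC-placebo is tested above 5% in every scenario examined: about 8% at SDs of 2:1:1 without session variance, and roughly 23-30% with moderate unmodelled session variance. The direction for CBD-placebo is not fixed: about 0.5-0.8% at 2:1:1 when session variance is absent or modelled with a common variance, and about 6-18% when it is present and unmodelled.

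These sizes rest on assumed SD and session-variance ratios, 15 completers with complete data, and a contrast averaged over the post-dose ratings. The mechanism needs only the model as stated. It is a cheap improvement worth making before the data are analysed.

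**What to change.** In the Data Analytic Plan, under Cannabis Effects, state one of these:

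1. Each active-placebo contrast is tested on participants' own active-minus-placebo differences (14 df with 15 completers).
2. The mixed model includes a participant-by-condition term, with condition-specific session and residual variances and a named small-sample df method. Condition-specific residual variances alone are not enough if session variance is present.

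Make the planned comparisons in the Data Analysis paragraph of Study Procedures use the same error term, so that the two descriptions agree.

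**Cost.** One sentence in each place. With equal variances and complete data, option 1 costs about 3 points of power and intervals about 5% wider. It also drops anyone who lacks one of the two sessions, which matters because the continuation report records two discontinuations among five enrolled. Option 2 keeps partial data but estimates six condition-specific variances plus the intercept variance from about 15 people, so it may fail to converge. Naming option 1 as the fallback would cover that.

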Laboratory Sessions: Participants will be instructed that they should not smoke either marijuana or cigarettes on the morning of a session (beginning at midnight). We will do a carbon monoxide (CO) test upon their arrival in the laboratory to verify nothing was recently smoked. Participants will also be given a breathalyzer test to ensure that they did not drink alcohol prior to arrival. At each visit, urine samples will be tested for drug use, and, for women of child-bearing age, for pregnancy. Subjects who are found to be pregnant will be discontinued from the study, but will receive payment for those procedures that they have already completed. Participants with high COs or those testing positive for drugs other than marijuana will be re-scheduled and possibly excluded from further participation. Patients will then receive either high THC (5-10%)/low CBD (<1%) marijuana, low THC (<1%)/high CBD (>10%) marijuana, or placebo (0% THC and CBD). The marijuana used in the study will be provided by the NIDA. We will guide participants through smoking individual puffs of marijuana using cue-dosing procedures until 50% of the cigarette has been smoked. Specifically, for each puff, participants will be instructed to inhale for 5 seconds and hold each puff in the lungs for 10 seconds. There will be approximately a 40-second interval between each puff. For the first hour after marijuana administration, clinical ratings, scales, and BP/HR will be obtained every 20 minutes. During the second hour, these measures will be repeated once every half-hour, and then again at the conclusion of the third hour (see Table 1). The session will end after the third hour. Participants will be allowed to leave the facility when they pass the field sobriety test, and will be instructed not to drive a car or use other drugs or alcohol for at least 8 hours after marijuana administration.

Table 1. Session Schedule

| TIME (min) | EVENT |
|------------|--|
| -50 | CO, collect urine, breathalyzer, start breakfast |
| -30 | Finish breakfast (set timer for 30 min), balance, TLFB, BP/HR, VAS, YBOCCS, STAI |
| 0 | Marijuana administration |
| 20 | BP/HR, VAS, YBOCCS, MRF, STAI |
| 40 | BP/HR, VAS, YBOCCS, MRF, STAI |
| 60 | BP/HR, VAS, YBOCCS, MRF, STAI |
| 90 | BP/HR, VAS, YBOCCS, MRF, STAI |
| 120 | BP/HR, VAS, YBOCCS, MRF, STAI |
| 180 | BP/HR, VAS, YBOCCS, MRF, STAI, Field Sobriety Test, participant discharge |

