** BP/HR = blood pressure and heart rate; VAS = Visual Analogue Scale; YBOCCS = Yale-Brown Obsessive-Compulsive Challenge Scale; MRF = Marijuana Rating Form; STAI = State/Trait Anxiety Inventory; TLFB = Marijuana Timeline Followback

Patients will be required to take public transportation to and from the laboratory each session, for which they will be reimbursed. Study clinicians will conduct the Field Sobriety Test. After confirming that the participant has passed the Field Sobriety Test, the patient will be allowed to leave the laboratory. If a participant is still impaired at the end of the session, she or he will be asked to remain in the laboratory until the effects wear off, and will be paid extra (i.e. \$10 per hour for any additional time in the laboratory). In the event that the impairment does not resolve in a timely manner, a study physician will determine whether the person can leave the laboratory or if further action is needed. It is worth noting that in our experience, it is exceedingly rare (<1% of all participants) for marijuana smokers to remain intoxicated several hours after smoking marijuana in the laboratory.

Laboratory Facility: Experimental sessions will be conducted in the Substance Use Research Center (SURC) located on the 3rd floor of the NYS Psychiatric Institute.

Safety Measures: Vital signs (heart rate and blood pressure) will be monitored in each session. If SBP > 180 mmHg, DP > 110 mmHg, or HR > 120 bpm, these measures will be taken 2 additional times at 2 min intervals: A physician will see the participant immediately if blood pressure or heart rate remain above these levels for 3 continuous readings.

Data Analysis: A between and within-subject repeated measures analysis of variance (ANOVA) with planned comparisons will be implemented to determine the effects of marijuana on OCD symptoms

You can upload charts or diagrams if any

Criteria for Early Discontinuation

Criteria for Early Discontinuation

Participants are free to withdraw from the study at any time for any reason. Study doctors are to discontinue patients from the study if patients:

- Request an early discontinuation or withdraw consent.
- Experience a serious or intolerable adverse event that prevents the patient from continuing.

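### Read naturally, the mixed model (one straight line per condition, participant as the only random unit) gives time-point contrasts with intervals that are too narrow and, unless the drug difference is linear, biased; the role of the -30 min reading is unstated

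*Combined protocol and SAP*

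**What the plan says.** The Cannabis Effects paragraph of the Data Analytic Plan opens: "We will use a random-effects linear mixed model to evaluate changes in each continuous outcome". The outcomes it lists are YBOCCS, OCD-VAS, STAI-S, MRF and cardiovascular measures. Participants are the random effect, and the other terms are "condition and time as fixed within-subjects factors, the interaction between condition and time, and a random intercept". On time it says: "Given that the interval between sessions increases over the course of each session, we will model time as a continuous variable". (I read this as the intervals between readings within a session.) Contrasts from the fit are then to "estimate differences in outcomes between both active cannabis varieties and placebo at different time points".

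Table 1 (Study Procedures) gives one pre-dose row, at -30 min: "Finish breakfast (set timer for 30 min), balance, TLFB, BP/HR, VAS, YBOCCS, STAI". The post-dose rows, at 20, 40, 60, 90, 120 and 180 min, each list "BP/HR, VAS, YBOCCS, MRF, STAI". MRF therefore has six readings per session and the other outcomes have seven.

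The Data Analysis paragraph under Study Procedures names a different method: "A between and within-subject repeated measures analysis of variance (ANOVA) with planned comparisons will be implemented".

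**The concern.** Three things are left open, and the time-point contrasts depend on all of them. They are the only effect estimates the plan states.

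- **Form of time.** Continuous time with a condition-by-time interaction and no further term is naturally one straight line per condition. Uneven spacing does not require this, because every session shares the same nominal times and categorical time handles any spacing.
- **The -30 min row.** The text points both ways. Increasing intervals describe the post-dose schedule: counted from dosing, the gaps are 20, 20, 20, 30, 30 and 60 min. With -30 min kept, the first gap between rows is 50 min. On the other hand, the model is meant to evaluate changes, and the pre-dose reading exists for every listed outcome except MRF.
- **Random terms.** Each condition is given in its own session on its own day. With the participant as the only random unit, two readings 20 minutes apart count as no more alike than two readings from different days. Any day-to-day variation enters the drug comparison without entering its standard error.

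At stake are the size, timing and stated precision of the effects. The same data could also give different answers depending on choices the plan does not record.

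**Working it through.** The plan gives no figure on this point to reproduce.

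**Inputs from the documents:** the Table 1 times; three sessions per person, one per condition; 15 completers; two-sided alpha 0.05.

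**Assumed:** complete data on 15 people; within-person variance of 1 for a single reading, of which a share s is common to all readings of a session; difference curves scaled to a peak of -1.

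**(a) Interval coverage: straight line, participant intercept, six post-dose rows**

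- Mean time is 85 min and the sum of squares about it is 17,150. The leverage of time t is h = 1/6 + (t - 85)²/17,150, which is 0.168 at 90 min and 0.693 at 180 min.
- True contrast variance = (2/15) × [s + (1 - s)h].
- The model reports (2/15) × v × h, where v is the pooled within-person residual variance. There are 15 × 3 × 6 = 270 rows and 270 - 15 - 5 = 250 residual df. On average v = [14 × 12 × s + 250(1 - s)]/250.
- Coverage ≈ 2Φ(1.96r) - 1, with r = √{v h / [s + (1 - s)h]}.
- For s = 0.4, v = (67.2 + 150)/250 = 0.869.
  - At 90 min, r = √(0.869 × 0.168 / 0.501) = 0.54 and coverage is 71%.
  - At 180 min, r = √(0.869 × 0.693 / 0.816) = 0.86 and coverage is 91%.

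Simulation with 6,000 trials per cell agrees to within about a point:

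| Session share | Coverage over the six times, difference zero or exactly linear |
|---|---|
| 0% | 95% |
| 20% | about 82-93% |
| 40% | about 70-91% |
| 60% | about 61-89% |

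Under no drug effect at a 40% share, this means false-positive rates of about 9-30% instead of 5%.

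**(b) Bias of the line**

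With balanced data, the expected fitted difference is the least-squares line through the true difference.

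*With -30 min as an outcome row, flat effect of -1.* Mean time is 480/7 = 68.57, the sum of squares is 28,485.7 and the mean difference is -6/7 = -0.857. The slope is -98.57/28,485.7 = -0.00346 per min.

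- At 20 min: -0.857 + 0.168 = -0.69.
- At 180 min: -0.857 - 0.386 = -1.24.

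A 60-min peak (-0.4, -0.8, -1, -0.8, -0.5, -0.1) is fitted as -0.50 to -0.53 at every time.

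*Post-dose rows only, same 60-min peak.* Mean is -0.6 and slope is 56/17,150 = 0.00327. The fit at 20 min is -0.6 - 0.212 = -0.81 against a true -0.4. At 60 min it is -0.68 against -1.

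| True difference (assumed) | Largest error, post-dose rows only |
|---|---|
| Zero, flat or linear | 0 |
| Early, nearly linear decline (-1, -1, -0.8, -0.5, -0.3, 0) | 0.09 |
| Exponential decay from 20 min, half-life 60 / 30 / 20 min | 0.11 / 0.24 / 0.34 |
| 60-min peak: curve above / smoother gamma shape | 0.41 / 0.27 |
| 90-min peak (-0.2, -0.5, -0.8, -1, -0.8, -0.4) / smoother gamma shape | 0.38 / 0.26 |

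With the 20-min half-life, the fit at 180 min is +0.20 where the true value is about 0, so the sign is wrong.

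**(c) Bias and intervals together**

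- With no session variance and a peak of 1 within-person SD, coverage of the line is about 58% (20 min) and 54% (60 min) for the 60-min peak, and 67% (20 min) and 30% (90 min) for the 90-min peak. At 0.5 SD these become about 75-88%, and at 0.3 SD about 88-93%.
- At a 40% share, adding a participant-by-session intercept but keeping the line still gives 74% and 78% for the 1 SD 60-min peak. Adding it with categorical time gives 95-96% at every time.

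**The case against.** **The plan does not say straight line.** True. A spline or polynomial would also be continuous time. But then its form is missing, so there is a gap either way. It also cannot be excluded that the separate mention of a random intercept was meant to cover sessions, but no session unit is named.

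**A reader might infer that the contrasts are bound to be wrong, or that the line itself produces false positives.** The documents support neither. They give no time course for OCD symptoms. A misfitted line is still right where it crosses the true curve, and with no drug effect it is unbiased. The excess false positives in (a) come from the missing session term, not from the line. Nor may one assume that an early peak costs little: that depends on how fast the effect fades.

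**A line may be a sensible choice at 15 completers.** This stands in part. A single-time categorical contrast has SE √(2/15) = 0.365. At a 40% session share and a 0.5 SD 60-min peak, the line's error at 20 min has bias 0.206 and SE 0.294, so root-mean-square error √(0.042 + 0.086) = 0.36, slightly lower. At a 1 SD peak it is √(0.170 + 0.086) = 0.51, clearly worse. Choosing between a line and categorical time for post-dose rows is therefore partly preference.

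**With categorical time the session intercept matters little for single-time contrasts.** Correct as far as it goes: coverage is then 92-95% with a participant intercept alone. But the stated model has continuous time, where the loss is large. Under categorical time, a post-dose average would still cover only about 83, 72 and 63% at 20, 40 and 60% share.

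**Keeping -30 min as an outcome row is harmless under categorical time.** Also correct. The harm comes from running a straight line through it.

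**Conclusion.** The point holds as a specification fault that should be fixed, with medium confidence about its size.

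The firmer part is the random structure. Under the natural reading, any session-to-session variation makes the plan's own contrasts look more precise than they are, whatever the drug does. The bias is conditional: none for a zero or linear difference over the rows used, about 0.1 to 0.35 of the peak for early peaks, and 0.26 to 0.41 for 60- or 90-min peaks with post-dose rows only. If -30 min is an outcome row, even a flat effect is distorted.

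The curves, effect sizes and session shares are all assumed. Complete data on 15 people is also assumed, although the continuation report shows 2 of 5 enrolled participants discontinuing. With post-dose rows only, the average over the six times is the same under a line or categorical time, so the form of time does not affect it.

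The ANOVA and mixed-model statements conflict, but that is a separate matter and does not add to the bias argument.

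**What to change.** In the Cannabis Effects paragraph:

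1. Add a participant-by-session random intercept.
2. Model the six post-dose times with condition by categorical time, or with a pre-specified curve in post-dose minutes. Do not fit a straight line through the -30 min row.
3. State the role of the -30 min reading. One option is a session baseline covariate for YBOCCS, OCD-VAS, STAI-S and the cardiovascular outcomes. That is a gain in precision, not a bias correction, and MRF has no pre-dose value.

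Separately, reconcile the repeated-measures ANOVA in the Data Analysis paragraph with the mixed model.

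**Cost.** This changes SAP wording only; all readings are already scheduled. Categorical time adds 18 - 6 = 12 fixed-effect parameters against 270 post-dose rows. A quadratic adds 3, but still misfits the listed early, 60-min and 90-min curves by up to 0.09, 0.20 and 0.12. Single-time categorical contrasts are less precise than a line that happens to fit. The SE ratio is √{1/[s + (1 - s)h]}, so the SE is 15-73%, 11-41% and 7-22% larger at 20, 40 and 60% session share. Intervals will be wider than the present model would report, but with close to their nominal coverage.
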